## **4. INTRODUCTION**

### **4.1 BACKGROUND**

Bone anchor fixation devices are typically indicated for a variety of repairs in the shoulder, elbow, hand/wrist, hip, knee, and foot/ankle. There are numerous alternative therapy options associated with these indications including conservative therapies such as rest, non-steroidal anti-inflammatory drugs, injection of steroids with lidocaine, and physical therapy. Several clinical studies were identified that reported higher clinical outcome scores (9, 19), or the ability to return to previous level of activity (6, 9), or lower complication/re-injury rate (1, 9) in patients that were treated surgically rather than conservatively. When conservative therapy does not offer relief of symptoms for the patient, surgical intervention is often recommended. One method of surgical intervention is to repair using an implant such as an interference screw or suture anchor. Interference screws provide a press fit between bone to bone, or bone to graft/tendon whereas suture anchors approximate soft tissue with an implant embedded in the bone. The use of suture anchors may provide advantages such as reduced operative time, ease of access to the site of implantation, improved suture material, decreased stress along the suture line, greater repair strength, and improved consistency of load-to-failure characteristics (8, 10, 11, 18). Patient bone density, repair location, potential allergies, the operation being performed, and surgeon preference determine the size, type, and composition of the anchor needed to secure the soft tissue to the bone (5).

Suture anchors come in many diameters, lengths and materials, such as titanium, stainless steel, polyetheretherketone, or biodegradable absorbable materials such as polylactic acid and poly-L-lactic acid.

### **4.2 LITERATURE SUMMARY**

MINITAC◇ Ti 2.0 Suture Anchors from Smith & Nephew are metallic suture anchors. Metallic (stainless steel or titanium alloy) implants provide rigid, reliable fixation and have been used successfully for decades (5). They provide excellent fixation but can be associated with loosening and migration, which may lead to cartilage damage. Metallic implants can present postoperative

Study Protocol—Device	
Safety and Performance of MINITAC® Ti 2.0 Suture Anchor in Extremities	Number: MINI.PMCF.2018.11
	Version: 3.0, 20Aug19
	Page: Page 13 of 56

distortion of repaired tissue during radiographic assessment (22). As cited by Suchenski et al, the majority of bone anchors currently approved for clinical use are made of metal (20).

The use of metallic suture anchors in foot and ankle was evaluated by Molloy et al. and Petrera et al. (13, 15). The two studies reported on a total of 67 joints, with a mean follow up of 25-42 months. Molloy et al. reported one patient (5.5%) who complained of scar tenderness, and the suture was excised at 9 months (13). Symptoms were resolved after 6 weeks. Mean American Orthopaedic Foot & Ankle Society (AFOAS) scores improved from 53 to 96, and eight patients resumed normal pre-injury activity levels. Petrera et al. reported 6% of patients experienced minor complications which included two cases of superficial wound infection (4%), which resolved after oral antibiotic treatment, and one case of temporary neuropraxia (2%) of the superficial peroneal nerve (15). AFOAS scores improved from an average of 36 preoperatively to an average of 75.4 postoperatively. The pain subscale improved from 35 to 75, symptom subscale from 38 to 70, and QOL subscale from 35 to 75.

The use of metallic suture anchors in hand wrist and elbow was evaluated by Micic et al. and Iba et al. (7, 12). These publications reported on a total of 28 patients, with a mean follow up of 20.5 to 51 months. Micic et al. reported 13 patients (65%) presented with heterotropic calcification of the joint capsule and collateral ligaments postoperatively (12). Post-traumatic degenerative change was found in six patients (30%). However, in most patients, this was not clinically significant. Concentric stability was achieved in all patients, and 18 patients (75%) had a firm endpoint during the valgus stress test. Overall mean functional motor evoked potentials was 93.2. Iba et al. reported no patients who demonstrated continuing symptoms, and all patients had a stable metacarpophalangeal joint after surgery (7). Postoperative grip strength and pinch strength were increased compared with preoperative values. All patients returned fully to their pre-injury work or sporting activities within six months after surgery. Postoperative flexion was decreased by an average of six degrees, but no patients noted functional deficiency.

Study Protocol—Device	
Safety and Performance of MINITAC◇ Ti 2.0 Suture Anchor in Extremities	Number: MINI.PMCF.2018.11
	Version: 3.0, 20Aug19
	Page: Page 14 of 56

### **4.3 STUDY PURPOSE**

This is a retrospective study to evaluate intra-operative, 6 months and 12 months safety and performance of the MINITAC◇ Ti 2.0 Suture Anchors for extremities repair to meet post-market clinical follow-up requirements as outlined by the Notified Body (BSI).

### **4.4 SAFETY CONSIDERATIONS**

The MINITAC◇ Ti 2.0 Suture Anchor is intended to provide secure reattachment of soft tissue to bone in the foot and ankle as well as elbow, wrist and hand. Representative language of the contraindications and potential adverse effects from the MINITAC◇ Ti 2.0 Suture Anchor can be found in the Instructions for Use (IFU).

## **5. OBJECTIVE(S)**

### **5.1 PRIMARY OBJECTIVE**

The primary objective of this study is to assess safety and performance of the MINITAC◇ Ti 2.0 Suture Anchor in extremities over a time period of 6 months after intervention.

### **5.2 SECONDARY OBJECTIVE**

The secondary objective of this study is to assess safety and performance of the MINITAC◇ Ti 2.0 Suture Anchor in extremities over a time period of 12 months after intervention.

## **6. INVESTIGATIONAL PRODUCT(S)**

### **6.1 IDENTIFICATION**

#### **6.1.1 Investigational Product**

The MINITAC◇ Ti 2.0 Suture Anchor is designed to provide secure reattachment of soft tissue to bone in extremities. It is available in 2.0mm size with double suture configuration.

Suture anchors are manufactured out of a titanium alloy whereas the sutures are either braided, silicone or polytetrafluoroethylene impregnated, polyester, non-absorbable or braided, uncoated, ultra-high-molecular-weight (UHMW) polyethylene and UHMW polyethylene with monofilament

Study Protocol—Device	
Safety and Performance of MINITAC◇ Ti 2.0 Suture Anchor in Extremities	Number: MINI.PMCF.2018.11
	Version: 3.0, 20Aug19
	Page: Page 15 of 56

polypropylene cobraid, non-absorbable. The Mini TAC™ 2.0 mm suture anchors are available either with stainless steel needles preassembled to the insertion device or without needles.

**Figure 6.1-1: MINITAC◇ Ti 2.0 Suture Anchor**

MINITAC◇ Ti 2.0 Suture Anchors are intended for use in the foot and ankle, as well as elbow, wrist and hand. MINITAC◇ Ti 2.0 Suture Anchors are intended to be used for the following indications:

- Foot and Ankle
  - Hallux valgus repairs
  - Medial or lateral instability repairs / reconstructions
  - Achilles tendon repairs / reconstructions
  - Midfoot reconstructions
  - Metatarsal ligament / tendon repairs / reconstructions
- Elbow, Wrist, and Hand
  - Scapholunate ligament reconstructions
  - Ulnar or radial collateral ligament reconstructions
  - Lateral epicondylitis repair
  - Biceps tendon reattachment

Reference numbers for MINITAC◇ Ti 2.0 Suture Anchors allowed in this study can be found in section 21.3.

Study Protocol—Device	
Safety and Performance of MINITAC◇ Ti 2.0 Suture Anchor in Extremities	Number: MINI.PMCF.2018.11
	Version: 3.0, 20Aug19
	Page: Page 16 of 56

## **6.2 PRODUCT USE**

Each device is packaged with an IFU (Document ID 10600149, Rev. C; 1061081, Rev E; 1061170, Rev F and 10600403 Rev D) to ensure that the device is used properly and for the intended purposes.

## **6.3 PACKAGING AND LABELING**

A commercial product is being used as approved for this study. Labeling is done as per the standard commercial packaging.

## **6.4 PRODUCT ACCOUNTABILITY PROCEDURES**

This is a post-market study and no product accountability procedures will be applied.

## **6.5 SURGICAL TECHNIQUE**

The operative visit of this study is retrospective. The use of the MINITAC◇ Ti 2.0 Suture Anchors was performed per standard of care at the participating sites and in accordance with the IFU.

## **7. SUBJECT ENROLLMENT AND WITHDRAWAL**

### **7.1 SUBJECT POPULATION**

A minimum of 30 and a maximum of 50 subjects should be enrolled into the study at up to 3 sites.

### **7.2 INCLUSION CRITERIA**

Subjects will be considered qualified for enrollment if they meet the following criteria:

1. Subject has undergone extremities repair using the MINITAC◇ Ti 2.0 Suture Anchor.
2. Subject was  $\geq$  18 years of age at time of surgery.
3. Subject status is  $>$  12 months post-operative.

Study Protocol—Device	
Safety and Performance of MINITAC◇ Ti 2.0 Suture Anchor in Extremities	Number: MINI.PMCF.2018.11
	Version: 3.0, 20Aug19
	Page: Page 17 of 56

### 7.3 EXCLUSION CRITERIA

Any one (1) of the following criteria will disqualify a potential subject from participation in the study:

- |   |
|---|
| 
 
1. Subject is entered in another investigational drug, biologic, or device study or has been treated with an investigational product within 12 months post-operative.
 
 |
|---|

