### 7.4 SCREENING

Subject screening will include a retrospective chart review. To eliminate the potential for selection bias, Investigators will consecutively screen subjects that have undergone extremities repair using the MINITAC◇ Ti 2.0 Suture Anchor by date of surgery, starting from the earliest surgery date, moving forward in time, up until dates of surgery which are at least 12 months prior to the study start date at each site.

Participating study sites are required to document all screened subjects considered for inclusion in this study on the Screening and Enrollment Log. If a subject is excluded from the study, the reasons for exclusion will be documented on the Screening and Enrollment Log.

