## 8.2 STUDY ENDPOINTS

### 8.2.1 Primary Endpoint

Clinical success rate (%) of the MINITAC◇ Ti 2.0 Suture Anchor in extremities at 6 months post-operative with clinical success defined as extremity repairs without signs of device failure and/or re-intervention as assessed by the surgeon.

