### **8.3 METHODS USED TO MINIMIZE BIAS AND MAXIMIZE VALIDITY**

#### **8.3.1 Retrospective Consecutive Enrollment**

To minimize any potential for selection bias consecutive enrollment will be utilized to retrospectively enroll any subjects encountered that meet the inclusion/exclusion criteria. Consecutive enrollment will be performed starting at earliest surgeries moving forward in time.

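### The sole exclusion criterion selects on events after the index surgery, so a failed repair revised with an investigational product within 12 months drops out of the success rate

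*Protocol*

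**What the plan says.** Protocol 7.3, repeated in the synopsis, gives a single criterion with two limbs: "Subject is entered in another investigational drug, biologic, or device study or has been treated with an investigational product within 12 months post-operative". The limb chiefly at issue is the second, which catches a subject who "has been treated with an investigational product within 12 months post-operative". Meeting the criterion is decisive: "Any one (1) of the following criteria will disqualify a potential subject from participation in the study".

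Eligibility is judged late. Under 7.2 a subject must be more than 12 months past surgery, and under 7.4 and 9.1.2 screening is a review of the existing chart.

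The primary endpoint (8.2.1) counts as successes "extremity repairs without signs of device failure and/or re-intervention as assessed by the surgeon" at 6 months. The secondary endpoint (8.2.2) uses the same definition at 12 months. A re-intervention is therefore a failure in its own right.

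The protocol relies on consecutive sampling against selection bias. Section 7.4 states: "To eliminate the potential for selection bias, Investigators will consecutively screen subjects that have undergone extremities repair". Section 8.3.1 adds that "consecutive enrollment will be utilized to retrospectively enroll any subjects encountered that meet the inclusion/exclusion criteria".

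For excluded subjects, 7.4 asks for the reason on the Screening and Enrollment Log. Section 7.6 asks for demographics and the reason when ineligibility is found after consent or waiver. Neither asks for the outcome. The SAP (3.2.1) analyses enrolled subjects only, and SAP 5.3.4 plans no sensitivity analysis.

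**The concern.** In a retrospective series, eligibility should rest on facts fixed at or before the index operation. Here the second limb rests on what happened during follow-up, and one route to meeting it runs through failure of the repair. A repair that fails at month 4 and is revised with an investigational product is a failure under 8.2.1. It is then disqualified because of how that failure was treated. Consecutive screening cannot correct this, because 8.3.1 makes enrollment conditional on the same criterion.

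Two ambiguities add to the problem.

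- **No clear date on the first limb.** Being entered in another study could refer to the time of screening, the 12 months after surgery, or the time of surgery. Sites could differ.
- **A term with two uses.** Protocol Section 6, 6.1.1 and 21.3 use the term investigational product for the MINITAC anchor itself. Read that way, a revision with a second MINITAC anchor within 12 months could also trigger exclusion.

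At stake are the success rates, and also the safety summaries of re-interventions and device deficiencies. SAP 5.3.6 draws these from the same enrolled set.

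**Working it through.** **1. The plan's own figures.** Inputs from Protocol Section 11 are 95% success, ±10-point precision, and N of 30 to 50. Protocol 10.4.1 gives the interval as two-sided 95% Clopper-Pearson. Taking the stated probability as P(half-width ≤ 0.10):

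- N = 30: the half-width is 0.0857 at 29/30 and 0.1063 at 28/30, so at least 29 successes are needed. 0.95^30 + 30 × 0.05 × 0.95^29 = 0.2146 + 0.3389 = 0.5535 (stated 55.4%).
- N = 50: the half-width is 0.0989 at 44/50 and 0.1046 at 43/50, so at least 44 are needed. P(X ≥ 44) = 0.9882 (stated 98.8%).

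Both reproduce. Neither depends on the exclusion criterion, so no stated figure is wrong because of it.

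**2. Expected failures.** 0.05 × 30 = 1.5, and 0.05 × 50 = 2.5. With counts this small, one subject is visible in the rate.

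**3. Which way one exclusion moves the rate.** With S successes in N, removing one failure gives S/(N − 1), and removing one success gives (S − 1)/(N − 1). Take N = 30 and S = 28 at 6 months, so 28/30 = 93.3%.

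| Subject excluded | 6-month status | 6-month rate | Effect on 12-month rate |
|---|---|---|---|
| Failed at month 4, investigational revision by month 12 | Failure | 28/29 = 96.6% | Up |
| Failed at month 8, investigational revision by month 12 | Success | 27/29 = 93.1% | Up |
| Unrelated exposure, repair intact to month 12 | Success | 27/29 = 93.1% | Down |

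If the place of the excluded month-4 failure is taken by a success, the 6-month rate is 29/30 = 96.7%. At N = 50 with three failures, removing one moves 47/50 (94.0%) to 47/49 (95.9%).

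**4. If a share of failures is removed.** If a share q of failures is excluded and no successes are, the expected observed rate is p / (p + (1 − p)(1 − q)). The documents do not give q, so the full range is shown.

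| True rate p | q = 10% | q = 25% | q = 50% | q = 100% |
|---|---|---|---|---|
| 95% | 95.5% | 96.2% | 97.4% | 100% |
| 90% | 90.9% | 92.3% | 94.7% | 100% |

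At q = 0 the rate is unchanged. The same holds in expectation if successes and failures are excluded in equal proportion.

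**The case against.** The strongest case on the other side has five parts.

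- **The criterion has a sensible purpose.** Another investigational product during follow-up could confound the performance and safety data. This stands, and a sensitivity analysis can address it without excluding anyone.
- **The direction is not fixed.** A reader might infer that the bias is always toward success. The documents do not support that. The criterion is not tied to outcome, unrelated exposure can remove successes, and a month-8 failure is a 6-month success whose removal slightly lowers the primary rate. This stands in full.
- **The frequency is unknown.** Exclusion of a failure needs a failure, treatment with an investigational rather than a marketed product, and timing within 12 months. Failures managed with marketed products stay in, unless a second MINITAC anchor is read as investigational. This also stands.
- **Consecutive enrollment was only promised for eligible subjects, and exclusions are logged.** So it goes too far to say that the criterion defeats the consecutive design. But the log gives a reason and no outcome, so the effect on the rate cannot be recovered from it. SAP 5.4.2 does foresee subjects entered without meeting eligibility criteria, but that does not reach a subject excluded at screening.
- **The first limb may be limited to 12 months.** The time phrase can be read as governing both limbs, in which case later entry into an unrelated study excludes nobody. A reader might infer that subjects now in another study are certainly removed. The text only leaves this open.

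**Conclusion.** The concern holds as a design weakness. The second limb selects on post-operative events within the outcome window, it is applied when the outcome has already occurred, and nothing in the protocol or SAP brings back the outcome of a subject so excluded. Where exposure follows a failure that occurred by 6 months, the 6-month rate is raised. Where it follows a failure that occurred by 12 months, the 12-month rate is raised. For other exclusions the direction is open.

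The size cannot be computed. The shift of about 3.2 points at N = 30 (93.3% to 96.6%) assumes that exactly one of two failures was revised with an investigational product within 12 months. It shows how sensitive a series of this size is and does not estimate the bias, which may be zero. The change is still worth making, because the series is small, it is meant as post-market evidence for the Notified Body, and the wording is easily repaired.

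**What to change.** **Protocol 7.3 and synopsis.** Exclude only subjects who, at the time of the index surgery, were in another investigational study or were being treated with an investigational product other than the study anchor. This dates both limbs and settles the double use of the term.

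**Main analysis.** Keep subjects first exposed after the index surgery, and include their 6- and 12-month outcomes in the main success rate whether they failed or not. Count an investigational revision as a re-intervention. Counting exposed failures while setting aside exposed intact repairs would only create outcome-dependent selection in the other direction.

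**SAP 5.3.3 and 5.3.4.** Add one sensitivity analysis that leaves out every subject with post-operative investigational exposure. In the time-to-event analysis, censor at exposure if it preceded any failure.

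**Subjects already excluded.** Re-screen those logged under this criterion where the waiver or consent covers them. Protocol 7.5 requests the waiver for subjects who meet eligibility, so coverage of newly eligible subjects has to be confirmed. Report the number of any who cannot be re-screened.

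**Cost.** A short protocol amendment approved by the HREC/EC (Protocol Section 15), a matching SAP revision, and some re-screening. A few retained subjects may have later outcomes affected by another product, and the sensitivity analysis is there to show how much that matters.

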### 7.4 SCREENING

Subject screening will include a retrospective chart review. To eliminate the potential for selection bias, Investigators will consecutively screen subjects that have undergone extremities repair using the MINITAC◇ Ti 2.0 Suture Anchor by date of surgery, starting from the earliest surgery date, moving forward in time, up until dates of surgery which are at least 12 months prior to the study start date at each site.

Participating study sites are required to document all screened subjects considered for inclusion in this study on the Screening and Enrollment Log. If a subject is excluded from the study, the reasons for exclusion will be documented on the Screening and Enrollment Log.

### 7.5 INFORMED CONSENT

Study sites will obtain HREC/EC approval before any study specific activities are performed. The Investigator and the Participating Site shall treat all information and data relating to the Study disclosed to Participating Site and/or Investigator in this Study as confidential and shall not disclose such information to any third parties or use such information for any purpose other than the performance of the Study. The collection, processing and disclosure of personal data, such as patient health and medical information is subject to compliance with applicable personal data protection and the processing of personal data (16,17, 24).

Due to the retrospective nature of the study, a HREC/EC waiver of informed consent for study participation should be requested for those subjects who meet eligibility criteria. If allowed, the retrospective data set will be collected for these subjects. No prospective visits will be performed. In Australia, a waiver or alteration of the requirements for obtaining informed consent may be

Study Protocol—Device	
Safety and Performance of MINITAC® Ti 2.0 Suture Anchor in Extremities	Number: MINI.PMCF.2018.11
	Version: 3.0, 20Aug19
	Page: Page 18 of 56

granted by the HREC/EC under any of the following provisions set forth by the National Statement on Ethical Conduct in Human Research published by National Health and Medical Research Council, Australia (14):

- a) involvement in the research carries no more than low risk to participants
- b) the benefits from the research justify any risks of harm associated with not seeking consent
- c) it is impracticable to obtain consent
- d) there is no known or likely reason for thinking that participants would not have consented if they had been asked
- e) there is sufficient protection of their privacy
- f) there is an adequate plan to protect the confidentiality of data
- g) in case the results have significance for the participants' welfare there is, where practicable, a plan for making information arising from the research available to them
- h) the possibility of commercial exploitation of derivatives of the data or tissue will not deprive the participants of any financial benefits to which they would be entitled
- i) the waiver is not prohibited by State, federal, or international law.

If an HREC/EC waiver is not granted, then the informed consent shall be obtained from all study subjects according to ISO 14155:2011 guidelines and the latest version of the Helsinki Declaration (3, 23). All applicable national regulations will also be followed including but not limited to the National Statement on Ethical Conduct in Human Research in Australia and in Belgium, the Belgian law of 7 May 2004 related to experiments on Humans (2, 14). In this case, Informed consent will be obtained either by mail or over the phone.

By mail: The potential subject will be sent the informed consent form and information sheet from a member of the study team. If the subject has any questions regarding their participation in the study, they can contact a member of the study team. If the subject is willing to participate, they sign and date the informed consent form and mail it back to the study team. The Investigator or designee will countersign the Informed Consent form. A copy of the signed informed consent documentation will be provided to the subject by mail, a copy will be placed in the subject's medical record, with the original filed in the Investigator Site File.

Study Protocol—Device	
Safety and Performance of MINITAC® Ti 2.0 Suture Anchor in Extremities	Number: MINI.PMCF.2018.11
	Version: 3.0, 20Aug19
	Page: Page 19 of 56

If the subject is unable to read, the informed consent document and associated study information may be read aloud to the subject in the presence of an impartial witness. If possible the subject shall sign and personally date the informed consent form. Where this is not possible, due to difficulties in writing, the subject shall provide verbal consent to participate in the study. The witness shall then personally sign and date the informed consent form, attesting that the information was accurately explained and that the informed consent was freely given. The informed consent process and documentation will be in accordance with all local regulations.

Over the phone: Upon receipt of the the informed consent form and information sheet by mail a delegated member of the study team will contact the potential subject to inform the subject of the purpose of the study and the potential risks and benefits known. If the subject agrees to participate, informed consent is documented by the study team member who obtained informed consent on the Telephone Informed Consent Log. In addition, the subject will be sent a letter of confirmation of the phone conversation and study participation.

If a subject refuses participation, no further information will be collected. Reason for exclusion should be noted on the Screening and Enrollment Log.

